2.1.3.3 Exploratory endpoint(s)

Following recommendation from the meeting with Japan Health Authority (PMDA) in April 2019, exploratory analysis will be performed for disease activity in PMR, quantified by the PMR activity score (PMR-AS).

PMR-AS is calculated as: CRP (mg/dl) + VAS p (0-10) + VAS ph (0-10) + (MST (min) x 0.1) + EUL (3-0).

Visual analogue scale for pain (VAS p) is the patient’s assessment of pain from HAQ-DI assessment, and the visual analogue scale for physician’s assessment (VAS ph) is the physician’s global assessment of disease activity, MD-VAS. The exact duration of morning stiffness (MST) and the ability to elevate the upper limbs (EUL: 3 = none, 2 = below shoulder girdle, 1 = up to shoulder girdle, 0 = above shoulder girdle) are captured in the “PMR assessment” eCRF. CRP value is from laboratory measurements.

PMR-AS will be assessed at baseline, Week 12, Week 24, and Week 52.

Note that only binary MST duration was collected (≤ 45 mins OR > 45 mins) prior to the collection of exact MST duration implemented in June 2019. Missing exact MST duration will be imputed using the median of MST duration at visit for each MST category (≤ 45 mins and > 45 mins).

2.1.4 Safety endpoints

The safety analysis will be based on the reported adverse events (AEs), serious AEs (SAEs) and adverse events of special interest (AESIs) including but not limited to neutropenia, thrombocytopenia, elevations in hepatic enzymes leading to permanent discontinuation and tuberculosis, and other opportunistic infections. Other safety information, such as clinical laboratory data and vital signs will also be assessed.

Observation period

The observation period will be divided into 4 epochs:

- The **screening** epoch is defined as the time from the signed informed consent date up to the time prior to first dose of SC IMP.
- The **treatment** epoch is defined as the time from the first dose of the IMP to the last dose of the SC IMP in the DB period +13 days.
- The **residual treatment** epoch is defined as the time from the end of TREATMENT epoch to the last dose of the SC IMP +60 days.
- The **post-treatment** epoch is defined as the time after the last dose of SC IMP +60 days.

The rationale of having “last dose of SC IMP +60 days” as the end of follow-up in the residual treatment epoch is to capture the events observed within an approximately 5 half-lives of the last sarilumab SC IMP.

The treatment-emergent adverse event (TEAE) period includes both **treatment** and **residual treatment** epochs.

2.1.4.1 Adverse events variables

Adverse event observation period

- Pre-treatment AEs are AEs that developed or worsened or became serious from the signed informed consent date up to first administration of SC IMP
- TEAEs are AEs that developed or worsened or became serious during the TEAE period
- Post-treatment AEs are AEs that developed or worsened or became serious during the post-treatment period

All AEs (including SAEs and AESIs) will be coded to a “LLT”, “PT”, “HLT”, “HLGT”, and associated primary “SOC” using the version of MedDRA currently in effect at Sanofi at the time of database lock.

The occurrence of AEs (including SAEs and AESIs) will be recorded from the time of signed informed consent until the end of the study.

Any SAE brought to the attention of the Investigator at any time after the end of the study for the patient and considered by him/her to be caused by the IMP with a reasonable possibility, should be reported to the monitoring team.

Adverse event of special interest (AESI)

Adverse events of special interest will be flagged in the database. The AESIs and its search criteria are listed in [Table 3](#) below:

Table 3 – Protocol defined AESIs and search criteria

AESI flag	Search criteria
Clinically significant infections including: 
 • Opportunistic infections • Tuberculosis • Infections requiring prolonged medication • Infections requiring parenteral treatment 	Reported by the investigators on the AE CRF page with AESI box ticked.
Lab abnormalities including: 
 • ALT increase leading to permanent discontinuation • ANC decrease leading to permanent discontinuation • Thrombocytopenia leading to permanent discontinuation 	
ALT >= 3xULN	
Pregnancy	CRF checkbox: Pregnancy
Symptomatic Overdose	CRF checkbox: Symptomatic Overdose

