Sarilumab, a fully human immunoglobulin G1 (IgG1) monoclonal antibody, targets IL-6R and inhibits IL-6 signaling. In this study, PMR patients will be treated with sarilumab with CS in order to evaluate the efficacy and safety of sarilumab in patients with PMR.

The efficacy and safety of sarilumab have been evaluated in the phase 2 and phase 3 studies of the rheumatoid arthritis (RA) clinical development program across different segments of the RA populations, patients with sarilumab treatment showed clinically relevant and significant improvements compared with placebo or active comparator either in combination with methotrexate or as monotherapy, respectively. Based on the safety profile of sarilumab available to date and other biological DMARDs, important identified risks include serious infections, neutropenia, and hypersensitivity reactions; important potential risks to be considered with sarilumab administration, consistent with this class of therapy, include laboratory abnormalities and the potential clinical consequences, such as thrombocytopenia and the risk of bleeding, clinically evident hepatic injury with elevated hepatic transaminases, and lipid abnormalities and increased risk of MACE. Other potential important risks include increased risk of malignancy and gastrointestinal perforation.

In addition to clinical development for RA, sarilumab has also been studied in patients with ankylosing spondylitis and non-infectious uveitis. Overall, the safety observations from these studies were consistent with what has been observed in patients with RA.

The primary dose of sarilumab for this study/indication (ie, 200 mg subcutaneously [SC]) once every 2 weeks [q2w]) is selected based largely on the aggregate data from the sarilumab rheumatoid arthritis (RA) clinical development program.

Both 200 mg q2w and 150 mg q2w doses have demonstrated robust clinical efficacy responses in the Phase 3 RA clinical development program, and suppression of biological markers of disease and inflammation similar to those found in PMR patients. While the higher dose has a generally more favorable efficacy response, both doses have acceptable safety profiles (see Investigator Brochure for additional details). Therefore, the dose of sarilumab 200 mg q2w is more likely to provide beneficial effects for patients with PMR and is selected for further evaluation in this study.

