#### **11.4.3 Analyses of safety data**

The summary of safety results will be presented by treatment group. Incidence rates and exposure adjusted event summaries will be provided for categorical safety summaries.

All safety analyses will be performed on the safety population using the following common rules:

- The baseline value is defined generally as the last available value before randomization.
- The observation period to be used for the safety population is the TEAE period. The TEAE period is defined as the time from first dose of randomized study treatment to the last dose date of IMP +60 days.
- For quantitative safety parameters based on central laboratory/reading measurements, descriptive statistics will be used to summarize results and change from baseline values by visit and treatment group.
- The analysis of the safety variables will be essentially descriptive and no hypothesis testing is planned.

The following definitions will be applied to laboratory parameters, vital signs and ECG.

- The potentially clinically significant abnormality (PCSA) values are defined as abnormal values considered medically important by the Sponsor according to predefined criteria/thresholds based on literature review and defined by the Sponsor for clinical laboratory tests, vital signs, and ECG.
- PCSA criteria will determine which patients had at least 1 PCSA during the on-treatment period, taking into account all evaluations performed during the on-treatment period, including unscheduled or repeated evaluations. The number of all such patients will be the numerator for the on-treatment PCSA percentage.

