#### **11.4.3.1 Analysis of adverse event data**

Treatment-emergent AEs, treatment-emergent SAEs, TEAEs leading to treatment discontinuation and treatment-emergent AESIs will be summarized for each treatment group based on MedDRA coding of verbatim terms reported by investigators.

Adverse event incidence tables will present by system organ class (SOC) (sorted by internationally agreed order), high-level group term (HLGT), high level term (HLT) and preferred term (PT) sorted in alphabetical order for each treatment group, the number (n) and percentage (%) of patients experiencing an AE. Multiple occurrences of the same event in the same patient will be counted only once in the tables within a treatment period. The denominator for computation of percentages is the safety population within each treatment group.

Treatment-emergent AESI, by AESI category and PT, will show number (%) of patients overall, sorted by decreasing incidence of PT within each AESI category. The AESIs include, but are not limited to, the following categories and details of the MedDRA coding will be provided in the statistical analysis plan: Neutropenia, thrombocytopenia, infections, hepatic disorders, diverticulitis/GI ulcerations/GI perforations, elevation in lipids, systemic allergic reactions, malignancy, autoimmune or drug-induced lupus like syndrome and demyelinating disorders.

Death: The following deaths summaries will be generated:

- Number (%) of patients who died by study period (TEAE, on-study) summarized on the safety population by treatment received.
- Death in nonrandomized patients or randomized and not treated patients.
- TEAE leading to death (death as an outcome on the AE CRF page as reported by the Investigator) by primary SOC , HLGT, HLT and PT showing number (%) of patients sorted by internationally agreed order of SOC and alphabetic order of HLGT, HLT, and PT.

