#### 11.4.3.2.1.2 Assessment of potential drug-induced liver injury

The liver function tests, namely ALT, AST, alkaline phosphatase and total bilirubin, are used to assess possible drug induced liver toxicity. The proportion of patients with PCSA values at any post-baseline visit by baseline status will be displayed by treatment group for each parameter. The proportion of patients with PCSA values at any post-baseline visit will also be displayed by duration of exposure for each treatment group.

Time to onset of the initial ALT elevation ( $> 3$  x ULN), time to onset of the initial AST elevation ( $> 3$  x ULN), time to onset of the initial total bilirubin elevation ( $> 2$  x ULN), and time to first observation of ALT  $> 3$ ULN or Total Bilirubin  $> 2$  ULN (whichever comes first) will be analyzed using Kaplan-Meier estimates, using the midpoint of the time interval between the first assessment showing the elevation and the previous assessment, presented by treatment group. A graph of distribution of peak values of ALT versus peak values of total bilirubin will also be presented. Note that the ALT and Total bilirubin values are presented on a logarithmic scale. The graph will be divided into 4 quadrants with a vertical line corresponding to 3 x ULN for ALT and a horizontal line corresponding to 2 x ULN for total bilirubin.

Summarize the normalization by parameter (to  $\leq 1$  ULN or return to baseline) of elevated LFTs by categories of elevation (1- $< 3$  x, 3 x, 5 x, 10 x, 20 x ULN for ALT and AST, 1.5 x ULN for Alkaline phosphatase, and 1.5 x and 2 x ULN for total bilirubin), with following categories of normalization: never normalized, normalized after IMP discontinuation. Note that a patient will be counted only under the maximum elevation category. 1-3, 3-5, 5-10, 10-20,  $> 20$ .

The incidence of liver-related AEs will be summarized by treatment group. The selection of preferred terms will be based on standardized MedDRA query (SMQ) Hepatic disorder. Time to liver-related treatment discontinuation and time to liver death may also be provided based on hepatic disorder SMQ.

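### SAP Table 3 gives no special-interest grouping for six of the protocol's ten AESI analysis categories, and the SAP omits the promised exposure-adjusted and hepatic-SMQ summaries without declaring it

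*SAP*

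**What the plan says.** The protocol holds two AESI lists. Section 10.5.1.3 lists what investigators must report at once: pregnancy, symptomatic overdose, ALT at or above 3 times ULN, clinically significant infections, and ALT, neutrophil or platelet abnormalities that end treatment permanently. Section 11.4.3.1 gives a different list for analysis: "Neutropenia, thrombocytopenia, infections, hepatic disorders, diverticulitis/GI ulcerations/GI perforations, elevation in lipids, systemic allergic reactions, malignancy, autoimmune or drug-induced lupus like syndrome and demyelinating disorders". For these it says that "details of the MedDRA coding will be provided in the statistical analysis plan".

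The protocol makes two further commitments. Section 11.4.3: "Incidence rates and exposure adjusted event summaries will be provided for categorical safety summaries". Section 11.4.3.2.1.2: "The incidence of liver-related AEs will be summarized by treatment group", with terms selected by the hepatic-disorder SMQ.

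SAP 2.1.4.1, Table 3, follows the first list. Its criterion for infections is "Reported by the investigators on the AE CRF page with AESI box ticked", and the last row reads "CRF checkbox: Symptomatic Overdose". SAP 2.4.5.1 builds the AESI summaries from those criteria. SAP 2.1.4 describes AESIs in open-ended terms but gives no criteria for any further category.

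**The concern.** The task that the protocol handed to the SAP was not done: no AESI category has a MedDRA search. Tick boxes cannot fill the gap, because the protocol never asks investigators to flag the six absent categories as AESIs. Perforation is reported as an SAE and diverticulitis or ulceration as an AE (10.8.6), cancers are medically important events (10.5.1.2), and hypersensitivity is an AE or SAE (10.8.5).

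Some of these risks are ones the protocol singles out. Section 4 says "Other potential important risks include increased risk of malignancy and gastrointestinal perforation" and places hypersensitivity among the important identified risks. Section 10.8.6 notes that corticosteroids raise the risk of perforation, and the arms differ by design in steroid duration (14 against 52 weeks). A grouped comparison between arms is therefore of real interest. At stake is the completeness and readability of the safety report, not the efficacy result.

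**Working it through.** **1. Categories set side by side.** The third column gives SAP output outside the AESI tables. It covers both arms unless noted, and is in addition to the general TEAE tables.

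| Protocol 11.4.3.1 category | Row in SAP Table 3 | Other SAP output |
|---|---|---|
| Neutropenia | Only if treatment ended permanently | Maximal grade and time to onset (2.4.5.3) |
| Thrombocytopenia | Only if treatment ended permanently | Maximal grade and time to onset (2.4.5.3) |
| Infections | Clinically significant infections | None further |
| Hepatic disorders | ALT only | Liver tests, ALT-bilirubin plot (2.4.5.3) |
| Diverticulitis, GI ulceration, perforation | None | Serious TEAE tables for perforation; GTI Specific List, where perforation counts only without regular NSAID use (protocol Appendix D) |
| Lipid elevation | None | Time to LDL-C and cholesterol elevation, abnormality incidence (2.4.5.3) |
| Systemic allergic reactions | None | Discontinuation tables; SMQs by ADA status in the sarilumab group only (2.4.8) |
| Malignancy | None | Serious TEAE tables |
| Lupus-like syndrome | None | None further |
| Demyelinating disorders | None | Discontinuation tables, where severe disease stops treatment (protocol 10.4.3) |

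Without a row: 10 − 4 = 6. Lipid elevation has laboratory cover, so 6 − 1 = 5 categories lack any grouped comparison between arms. Of the four with a row, two are restricted to cases that ended treatment.

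In the extracted Table 3 the criterion cells beside the laboratory and ALT rows are blank. I read the tick-box criterion as a merged cell covering them. The count of six does not depend on that reading.

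**2. Exposure adjustment.** SAP 2.4.5.1 gives numbers and percentages on the safety population and, for AESIs, incidence by patient and by event. Patient-years appear only as an exposure total (2.4.3.1). SAP event tables with an exposure-adjusted rate: 0.

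The documents give no discontinuation figures by arm, so the effect can only be shown under assumptions. Suppose a fraction d of one arm stops early, spread evenly over the year, nobody stops in the other arm, and crude percentages are equal.

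- On treatment time, the rate ratio is 1/(1 − d/2). For d = 10%, 20% and 30% this gives 1/0.95 = 1.05, 1/0.90 = 1.11 and 1/0.85 = 1.18.
- On the TEAE period (last dose plus 60 days, SAP 2.1.4), with the last injection at Week 50, a completer contributes 350 + 60 = 410 days. An early stopper contributes on average 175 + 60 = 235 days. The ratio is 410/(410 − 175d), giving 410/392.5 = 1.04, 410/375 = 1.09 and 410/357.5 = 1.15.

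The two definitions give different answers, so a time-at-risk rule must be stated.

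**3. Hepatic AEs.** The SAP's hepatic section (2.4.5.3) has laboratory displays only. The SMQ-based summary of liver-related AEs is absent.

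**4. Declaration.** SAP 1.5 covers only the sample-size, significance-level and confidence-interval changes of amendment 02. SAP 1.6 adds COVID-19 summaries and the PMR activity score. Neither mentions any of the above.

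**The case against.** The strongest reply is that nothing disappears. A reader might infer that a perforation or a cancer would leave no trace, or would show only as isolated preferred-term lines. The documents do not support that. SAP 2.4.5.1 tabulates all TEAEs, serious TEAEs and TEAEs leading to discontinuation by SOC, HLGT, HLT and PT in both arms, so related terms are summed at three levels above PT. Only a category that cuts across those groupings stays scattered. Neutropenia and thrombocytopenia are graded from laboratory data for all patients, whether or not treatment stopped.

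A reader might also infer that the SAP alone departed from the protocol. In fact Table 3 reproduces 10.5.1.3 faithfully, including its limit on neutrophil and platelet events, and the protocol never reconciles that list with 11.4.3.1. Nor does every AESI rest on a ticked box: SAP 2.4.3.2 also defines overdose from dosing intervals. Finally, a crude AESI event rate could be approximated from the event counts and total patient-years.

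These points limit the consequence. They do not meet the commitments in 11.4.3, 11.4.3.1 and 11.4.3.2.1.2. No grouped search for malignancy, lupus-like or demyelinating events appears anywhere in the SAP, and allergic reactions have no placebo comparison by SMQ.

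**Conclusion.** The point holds as a gap in grouping and declaration, not as lost data. Six of ten protocol analysis categories have no AESI row and two more are narrowed. The substantive loss is the grouped between-arm comparison for five: malignancy, GI events, systemic allergic reactions, lupus-like syndrome and demyelination. Exposure-adjusted event summaries and the hepatic-disorder SMQ summary are also missing, and neither SAP 1.5 nor 1.6 says so.

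It should not be concluded that crude percentages will mislead in this trial. That depends on unequal time at risk, which the documents do not report. Under the assumptions shown, the distortion runs from about 4% to 18% for 10% to 30% one-sided discontinuation. The SAP should be corrected, but the primary analysis is untouched.

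**What to change.** 1. Reconcile the AESI lists of protocol 10.5.1.3 and 11.4.3.1, stating which governs reporting and which governs analysis.
2. Add to SAP Table 3 a named SMQ or HLT search for each of the ten analysis categories, tabulated in both arms whether or not the box was ticked.
3. Add patients with events per 100 patient-years for TEAEs, SAEs and each AESI category, with a time-at-risk rule consistent with the TEAE period in SAP 2.1.4.
4. Restore the hepatic-disorder SMQ summary of liver-related AEs.
5. For anything not restored, record it in SAP 1.6 as a departure from the protocol, with the reason.

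The cost is SAP wording and standard safety programming. AEs are already to be MedDRA-coded and patient-years already computed, so no new data are needed. The searches should be fixed before unblinding; any added later should be labelled so.

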2.1.4.2 Deaths

The deaths per the observation period will be summarized.

- Death on-treatment: deaths occurring during the treatment period (i.e., treatment Epoch)
- Death during follow-up: deaths occurring during the residual treatment period
- Death post-treatment: deaths occurring during the post-treatment period

2.1.4.3 Laboratory safety variables

Clinical laboratory data will include hematology, clinical chemistry, and urinalysis. Clinical laboratory values will be converted to standard international units; international units will be used in all listings and tables. In addition, the lipids parameters will also be summarized in US units.

Hematology and chemistry data will be collected at screening, baseline, Weeks 4, 12, 24, 40, and 52, and/or early termination unless otherwise specified. The laboratory parameters will be classified as follows:

- Hematology
 - **Red blood cells and platelets and coagulation:** hemoglobin, hematocrit, platelet count, red blood cell (RBC) count, and RBC morphology (if RBC count is abnormal).
 - **White blood cells:** white blood cell (WBC) count and WBC differential (neutrophils, lymphocytes, monocytes, basophils, eosinophils).
- Clinical chemistry
 - **Metabolism:** fasting lipids (total cholesterol, high density lipoprotein cholesterol (HDL-C), low density lipoprotein cholesterol (LDL-C), ratio of HDL-C versus LDL-C (HDL-C:LDL-C), triglycerides), total proteins, CRP, fasting glucose, and hemoglobin A1c (HbA1c).
 - **Electrolytes:** sodium, potassium, chloride, calcium, phosphate, and bicarbonate.

- **Renal function:** creatinine, creatinine clearance, uric acid, and blood urea nitrogen (BUN).
- **Liver function:** alanine aminotransferase (ALT)/SGPT, aspartate aminotransferase (AST)/SGOT, alkaline phosphatase (ALP), albumin, total bilirubin, conjugated and unconjugated bilirubin, and lactate dehydrogenase (LDH).
- **Pregnancy test:** Serum β -hCG for all women of childbearing potential (screening only).
- **TB screen:** QuantiFERON®-TB Gold evaluation.
- **Hepatitis screen:** Hepatitis B and C serology, human immunodeficiency virus serology.

Urine samples will be collected as follows:

- **Urinalysis – dipstick:** pH, specific gravity, blood, glucose, protein, nitrates, leukocyte esterase, and bilirubin. If any parameter on the dipstick is abnormal, a urine sample was to be sent to the central laboratory for testing.

A urine pregnancy test was done for all women of childbearing potential at baseline, all visits up to Week 52 or early termination.

2.1.4.4 Vital signs variables

Vital signs variables include: heart rate, systolic blood pressure, and diastolic blood pressure, height, weight, and body temperature.

2.1.4.5 Antinuclear antibodies

Antinuclear antibodies (ANA) will be measured at baseline and EOT visits.

2.1.5 Immunogenicity endpoints

The immunogenicity blood samples will be collected before injection during the same visit according to the Study Flow Chart ([Appendix A](#)).

Samples analyzed in the antidrug antibody (ADA) assay will be categorized as either positive or negative, and in the case of a positive result will be further characterized as either neutralizing or non-neutralizing.

ADA positive patient is defined as patient with at least one treatment-emergent or treatment-boosted ADA positive sample during the TEAE period, where

- Treatment-emergent ADA positive patient is defined as a patient with non-positive assay (meaning negative or missing) response at baseline but with a positive assay response during the TEAE period.

- Treatment-boosted ADA positive patient is defined as a patient with a positive ADA assay response at baseline and with at least a 4-fold increase in titer compared to baseline during the TEAE period.

ADA negative patient is defined as patient without a treatment-emergent or treatment-boosted ADA positive sample during the TEAE period.

A treatment-emergent positive response is further classified as persistent or transient.

Persistent ADA response: treatment-emergent ADA detected at two or more consecutive sampling time points during the TEAE period, where the first and last ADA positive samples are separated by a period of at least 16 weeks. Also persistent in case last sample analyzed is positive.

Transient ADA response: A treatment-emergent response that is not determined to be persistent.

